# C. Objectives, Aims, & Hypotheses

In response to NOT-OD-101: HEAL Initiative: Notice of Special Interest (NOSI) regarding the Availability of Administrative Supplements to Support Strategies to Reduce Stigma in Pain Management and OUD and Treatment, this project will evaluate an intervention to reduce stigma in PCCs by integrating stigma reduction training into the Opioid Wizard training. PCCs will be randomized to this novel stigma reduction training, grounded in stigma science, or an attention-control training. The overall goal of this project is to determine whether stigma reduction training reduces PCC stigma, increases intention to get waivered to prescribe buprenorphine or to prescribe buprenorphine if a waiver were no longer required, and ultimately increases the likelihood that PCCs use Opioid Wizard.

Aim 1: To examine whether a PCC training to reduce stigma toward people with OUD, compared to an attention-control training, reduces stigma, increases intention to get waivered, increases intention to prescribe buprenorphine if a waiver were no longer required, and increases the likelihood of using Opioid Wizard.

**H1a:** PCCs who are randomized to stigma reduction training will report less stigma towards patients with OUD compared to PCCs who are randomized to control training.

**H1b:** Among non-waivered PCCs, PCCs who are randomized to stigma reduction training will report greater intention to get waivered to prescribe buprenorphine than PCCs who are randomized to control training.

**H1c:** Among non-waivered PCCs, PCCs who are randomized to stigma reduction training will report greater intention to prescribe buprenorphine for OUD in the next year if a waiver were no longer required than PCCs who are randomized to control training.

**H1d:** PCCs who are randomized to stigma reduction training will use Opioid Wizard at a greater proportion of visits where the PCC is alerted to high risk than PCCs who are randomized to control training.

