- b. Study Setting. This administrative supplement will be implemented at HealthPartners. HealthPartners is the largest consumer-governed nonprofit healthcare organization in the country. HealthPartners has 55 primary care clinics and cares for more than 1.2 million patients in Minnesota and western Wisconsin. Patients are insured by a mix of insurance types, including Medicaid (12%), Medicare (12%), commercial insurance (60%) and others. At HealthPartners, approximately 7% of PCCs are currently waivered to prescribe buprenorphine. This study will be conducted in the 30 HealthPartners primary care clinics randomized in COMPUTE 2.0. Each randomized clinic has at least 3 eligible PCCs and 50 adult patients who are aged 18-75 years and have an OUD diagnosis, are prescribed a MOUD, or are identified by the opioid risk calculator as being at high risk of OUD. The proposed supplement fits well within the scope of the parent award.
- c. Study Design. This study will use a randomized controlled trial design, in which PCCs will be randomized to receive one of two trainings delivered via MyLearning: a stigma reduction training or an attention control training. Outcome assessments will occur immediately following the training delivery (PCC initial survey), at 3 months following training completion (PCC follow-up survey), and in the 6 months following the training (objective indicators of PCC Opioid Wizard use, waivered clinician prescribing behavior, and waiver status). See Figure 1 for a schematic of the study flow.

[figure not shown]

Figure 1. Study flow diagram.

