#### **G.** The Interventions

- **a. Intervention delivery.** Both the stigma reduction intervention and the comparison intervention will be delivered via MyLearning, an online learning platform that is available at HealthPartners. This training will be interactive, as PCCs will have the opportunity to participate in a case-based training on how to use the Opioid Wizard and will be able to click and interact with the training to demonstrate learning.
- b. Common intervention components in both trainings. General additional training in both groups will include science-based education about OUD and MOUDs and how to use Opioid Wizard, including where to review relevant chart history, making a diagnosis, choosing a treatment option, conducting follow-up, and caring for comorbid conditions. Medical record details relevant for providing care to four prototype patients at risk for or with OUD, such as age, gender, race/ethnicity, and comorbid conditions, will be presented to demonstrate aspects of the CDS.
- c. Stigma Reduction Training. Contact with a person sharing personal narratives (including a story of "on the way down" and "on the way up") are the most powerful interventions to reduce public stigma of health conditions. 38,39 For this study we have modified this approach for an online learning format. In addition to the training for Opioid Wizard described above, the stigma reduction intervention group will include patient narratives and recommendations for non-stigmatizing language. For example, one narrative is the story of a patient who developed OUD after taking opioids for an injury. PCCs will hear this patient story (e.g., a video of the "patient" (actor) telling their story embedded in the training), and the trainer will walk through how to use the CDS, including how to review relevant chart history, make a diagnosis, discuss treatment options, and conduct follow-up and care for comorbid conditions. The short narratives provide de-stigmatizing context and demonstrate CDS applicability to diverse populations, in addition to demonstrating aspects of the CDS.

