- d. Comparison (Control) Training will include the general components as above but omits a stigma reduction component. This comparison training controls for attention, contact time and extra training on using Opioid Wizard. Participants will see the same cases that are presented in the Stigma Reduction Training, but they will not see the patient videos or hear the narratives. Instead, they will just see the EHR and the trainer will talk about the cases in generalities (e.g., "This is a patient who is coming in to the clinic who is at high risk for opioid use disorder.").

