#### H. Outcome assessment

**a.** Timing of outcome assessment. Immediately following training, PCCs will be asked to complete a brief (15-minute) follow-up survey via REDCap, a secure data

management software, to assess self-reported outcomes: stigma, waiver status, and, among non-waivered PCPs, intention to get waivered and intention to prescribe buprenorphine should a waiver no longer be required (see **Appendix D**). In addition, at 3 months following the training, PCCs will be asked to complete a follow-up survey via REDCap, to assess endurance of the stigma training on PCC stigma and intentions (see **Appendix E**). Opioid Wizard use will be pulled from CDS meta-data for each randomized clinician for encounters that are eligible for the Opioid Wizard intervention. PCC prescribing (number of MOUD, naloxone, and opioid prescriptions and the number of unique patients receiving prescriptions) and referral behavior will be extracted from the EHR. We will pull patient demographic information from the EHR to assess the extent to which provider behaviors differ across patient sub-groups, such as racial/ethnic groups, sex, and reason for intervention eligibility.

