# L. Sample size

There are 449 PCCs in the 30 clinics being considered for randomization to the parent study, COMPUTE 2.0, with an average of 15 per clinic (range 4-36). To the extent that the parent study will seek balance between treatment arms in clinic size, and by extension number of PCCs, we estimate that 225 PCCs will be in intervention clinics and eligible for this study. We have estimated power for PCC participation rates of 50%, 65%, and 80% with equal numbers of PCCs per arm. Approximately 93% of PCCs at HP are not waivered, which would reduce available sample sizes for H1b and H1c to 208 PCCs. The power analysis was calculated using G\*Power 3.1 and determined the minimal detectable standardized effect between groups for each outcome given available sample size,  $\alpha_2$  = .05, and desired power (see Table 1). Given these assumptions, we will have the ability to detect moderate differences (80% power: d = 0.42-0.55; RR=1.28-1.58) between the groups.

For Aim 2, the regression models will include PCCs in both arms and up to 4 covariates. Given sample size,  $\alpha_2$  = .05, and desired power, we will have adequate power to detect small effects for H2a (80% power:  $f^2$  = 0.05-0.08) and moderate effects for H2b (80% power: RR=1.29-1.60).

Table 1. Minimal detectable	Table 1. Minimal detectable standardized effects based on PCC						
participation rate and desired power.							
PCC participation= 50% 65% 80%							

	112 F	PCCs	146 F	PCCs	180 F	PCCs	
ро	wer =	0.80	0.90	0.80	0.90	0.80	0.90
H1a: OUD Stigma	d	0.49	0.57	0.47	0.54	0.42	0.49
H1b, H1c: Intentions	d	0.55	0.64	0.48	0.56	0.44	0.51
H1d: CDS Use: 30%	RR	1.58	1.69	1.50	1.59	1.44	1.52
50%	RR	1.44	1.51	1.38	1.44	1.34	1.39
70%	RR	1.36	1.43	1.31	1.37	1.28	1.33
H2a: Intentions	f 	0.08	0.10	0.06	0.08	0.05	0.06
H2b: CDS Use: 30%	RR	1.60	1.71	1.52	1.61	1.46	1.54
50%	RR	1.45	1.53	1.39	1.46	1.35	1.41
70%	RR	1.37	1.44	1.32	1.38	1.29	1.34
Note. Cohen's d = d; Co	hen's	$f^2 = f^2; I$	Rate ra	tio = RF	₹.		

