# M. Analysis Strategies

All variables will be examined using descriptive statistics and graphical methods to examine distributions, potential outliers, and analysis assumptions across and within study arms. The hypotheses predict that PCCs in the stigma reduction intervention will report less stigma of people with OUD and greater intentions to get waivered and prescribe buprenorphine (among non-waivered PCCs), and will use Opioid Wizard at a greater proportion of eligible encounters. A generalized linear model framework will be used to test the Aim 1 hypotheses, using appropriate error distributions and link functions to normalize outcomes. For H1a through H1c, the primary outcomes will be stigma (H1a) and intentions to get waivered (H1b) and to prescribe buprenorphine (H1c), assessed immediately following the training; as a secondary outcome, we will examine whether the intervention has enduring effects on stigma and intentions by examining differences assessed at the 3-month follow-up survey. Secondary analyses will include an interaction term between intervention arm and waiver status to assess treatment heterogeneity.

In Aim 2, multiple linear regression models, controlling for PCC characteristics (i.e., age, gender, PCC type [physician, nurse practitioner, physician assistant], and waiver status [H2b only]) will be used to examine whether self-reported OUD stigma is related to (1) intention to get waivered to prescribe buprenorphine and (2) Opioid Wizard use. Secondary analyses will include an interaction term between stigma and waiver status to examine whether waiver status moderates the association between stigma and Opioid Wizard use.

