In secondary analysis, we will examine whether self-reported stigma mediates the effect of the intervention on Opioid Wizard use. If the intervention affects Opioid Wizard use (H1d), and stigma is related to Opioid Wizard use (H2b), we will use a product of coefficients approach to quantify how much of the intervention effect is mediated by stigma. In other exploratory analyses, we will examine whether PCCs in the stigma reduction arm prescribe MOUD and /or naloxone to eligible patients at a higher rate than PCCs in the comparison arm, controlling for pre-Opioid Wizard prescribing behavior. We will also examine whether PCCs in the stigma reduction arm prescribe opioids to eligible patients at a lower rate than PCCs in the comparison arm, controlling for pre-Opioid Wizard prescribing behavior. Further, as a follow-up to H1b, we will examine whether PCCs in the stigma reduction arm are more likely to get waivered than control PCCs using a logistic regression framework. To understand how PCC experience with patients at high risk for problems with opioids may have influenced their decision to participate in this study, we will compare PCC prescribing and referral behaviors among PCCs who completed the training to those who did not among all randomized PCCs.

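### The H2a and H2b models pool both arms without adjusting for arm, although stigma is measured only after training, so an arm effect that bypasses stigma would leak into the stigma slope

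*Combined protocol and SAP*

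**What the plan says.** Section L states that for Aim 2 "the regression models will include PCCs in both arms and up to 4 covariates". Section M says the models examine whether self-reported stigma is related to intention to get waivered (H2a) and to Opioid Wizard use (H2b), "controlling for PCC characteristics (i.e., age, gender, PCC type [physician, nurse practitioner, physician assistant], and waiver status [H2b only". That makes three named covariates for H2a and four for H2b, so H2b already uses the stated maximum. Arm is in neither list.

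There is no pre-training survey. Section D.c says "Outcome assessments will occur immediately following the training delivery (PCC initial survey), at 3 months following training completion (PCC follow-up survey", and Section H.a says "Immediately following training, PCCs will be asked to complete a brief (15-minute) follow-up survey via REDCap". Stigma and intention therefore come from the same post-training questionnaire.

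Section C predicts that "PCCs who are randomized to stigma reduction training will report less stigma towards patients with OUD" (H1a), with higher intention (H1b) and higher tool use (H1d) in the same arm. Section M then makes H2b one of two conditions for mediation: if the intervention affects use (H1d) and "stigma is related to Opioid Wizard use (H2b), we will use a product of coefficients approach". It does not give the outcome model that supplies the stigma coefficient.

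**The concern.** The Aim 2 predictor is a post-randomisation variable that the trial is designed to move, and both Aim 2 outcomes are also expected to differ by arm. In a pooled model without arm, PCCs in the stigma reduction arm would tend to have lower stigma and higher intention or use. That alone produces a negative slope, even if stigma and behaviour are unrelated within each arm.

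This needs an arm effect on the outcome that does not pass through measured stigma. The design narrows such routes: "This comparison training controls for attention, contact time and extra training on using Opioid Wizard". It does not exclude them. Section G.c says of the stigma arm's content that "The short narratives provide de-stigmatizing context and demonstrate CDS applicability to diverse populations, in addition to demonstrating aspects of the CDS", which is a tool-use route, while Section G.d has control PCCs hear the cases discussed only in general terms. Any change in attitude that the six difference and disdain items miss would also act as a direct arm effect.

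At stake is whether H2a or H2b is declared supported partly because of arm, and whether the mediation step is triggered on that basis. If the bypassing effect raises intention or use, the bias favours H2a and H2b; if it lowers them, the bias masks a real association.

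**Working it through.** **1. Reproduce the plan's H2a figure.** Inputs from Section L: two-sided alpha 0.05, participation 50%/65%/80%, 208 non-waivered PCCs, hence N = 104/135/166. The test is for one coefficient in a linear regression (noncentral F, λ = f²·N, numerator df 1, denominator df N − k − 1).

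| Power | Computed f² | Table 1 |
|---|---|---|
| 80% | 0.077 / 0.059 / 0.048 | 0.08 / 0.06 / 0.05 |
| 90% | 0.103 / 0.079 / 0.064 | 0.10 / 0.08 / 0.06 |

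Table 1 reproduces. The 80% values are the same to three decimals with k = 4 or k = 5 predictors.

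**2. Bias formula.** With 1:1 arms (variance of arm = 0.25), let arm lower stigma by d_S and raise the outcome by d_Y outside stigma, both in within-arm SD units. If the within-arm slope is zero, the pooled slope is

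−0.25·d_S·d_Y / (1 + 0.25·d_S²).

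**3. Worst case for H2a (assumed).** Take d_S and d_Y from the H1a and H1b rows of Table 1 at 80% power, with d_Y wholly outside stigma. N here is 0.93 × 112/146/180 = 104/136/167; rounding from 208 instead gives 104/135/166, which makes no material difference.

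- 50%: 0.25 × 0.49 × 0.55 / (1 + 0.25 × 0.49²) = 0.0674 / 1.0600 = 0.064
- 65%: 0.25 × 0.47 × 0.48 / (1 + 0.25 × 0.47²) = 0.0564 / 1.0552 = 0.053
- 80%: 0.25 × 0.42 × 0.44 / (1 + 0.25 × 0.42²) = 0.0462 / 1.0441 = 0.044

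These are absolute values; the sign is negative. The corresponding f² is 0.004/0.003/0.002.

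**4. Rejection rate when the within-arm slope is zero** (simulation, 40,000 replicates; stigma and intention normal and independent given arm).

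| Scenario | 50% | 65% | 80% |
|---|---|---|---|
| Worst case, arm omitted | 10.1% | 9.4% | 9.0% |
| Half of d_Y bypasses stigma, arm omitted | 6.3% | 6.1% | 5.9% |
| d_S = d_Y = 0.2, arm omitted | 5.1% | 5.1% | 5.1% |
| Worst case, arm included | 5.1% | 5.1% | 5.0% |

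A repeat run agreed within simulation error (worst case 10.0%/9.7%/8.9%).

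**5. No bias under full mediation.** With a true slope of −0.30 and no direct effect, the pooled slope averages −0.301/−0.300/−0.300.

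**6. Bias when a real association exists.** With a true slope of −0.28, N = 104, d_S = 0.55 and a direct effect of 0.3 SD, the slope averages −0.319 without arm and −0.281 with it.

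**7. Sensitivity to inputs.** Table 1's H1a value of 0.49 at 112 PCCs does not reproduce: 56 per arm gives 0.53. Using 0.53 with d_Y = 0.55 moves the worst case only to about 10.5%. A wider assumed grid (d_S 0.30–0.55, direct effect 0.2–0.5 SD, N 104–166) gives 5.3% to 13.1%.

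**8. H2b.** Not quantified. The documents give no between-PCC spread of tool use, so a direct effect cannot be put on an SD scale.

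**The case against.** The strongest reply is that H2a and H2b are worded as associations. If arm produces a pooled association, rejecting is correct for the hypothesis as written, and 9–10% is an error rate only if the target is the within-arm slope. That stands as a point about the estimand. But the pooled association then depends on the trial's own 1:1 mix of two trainings, whereas a reader will take it as evidence that stigma relates to behaviour among PCCs. The plan should say which slope it reports.

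Second, the worst case is extreme, and the one non-stigma route visible in the text bears on tool use (H2b), whereas the figures are for H2a. Both arms also get the same tool training and see the same cases. This stands: the partial-bypass rows are more plausible than the worst case, and with a quarter bypassing the rate is about 5.1–5.4%.

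Third, the covariate list itemises PCC characteristics, so arm is not explicitly barred, and H2a has room for one more covariate. That is fair, but an analyst following the text would fit the model without arm.

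Fourth, the mediation analysis also needs a positive H1d and its outcome model is unspecified. Also true: its estimate is biased in this way only if the stigma coefficient comes from the arm-free H2b model. But the H1d condition means the H2b gate matters only when arm appears to affect use, which is when omitting arm can do harm.

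Finally, adjusting gives up the between-arm variation in stigma, which is useful information if training acts only through stigma. The loss is small and is costed under the fix.

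**Conclusion.** The concern holds, conditionally. Bias requires that arm shifts stigma and also shifts the outcome by a route outside measured stigma. For H2a, the Table 1-based worst case gives a spurious slope of 0.044–0.064 SD and a false-support rate of about 9–10%; the rate is about 6% at half bypass and about 5% for 0.2 SD effects. The spurious f² of 0.002–0.004 is roughly one-twentieth of the detectable 0.05–0.08. All arm effects used are assumptions, not trial data, and H2b is unquantified. The randomised Aim 1 comparisons are not affected. The change is worth making because the predictor is post-randomisation, H2b gates the mediation analysis and the remedy is cheap; the flaw does not undermine the trial.

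**What to change.** Three short edits:

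- In Section M, add study arm as a covariate in all H2a and H2b models, and state that the reported stigma slope is the within-arm one.
- In Section L, raise the stated maximum number of Aim 2 covariates from 4 to 5.
- In Section M's mediation paragraph, state that the stigma coefficient comes from an outcome model that includes arm.

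The cost is one degree of freedom. The detectable H2a f² at 80% power stays at 0.077/0.059/0.048, so Table 1's 80%-power entries for H2a do not change. If arm shifts stigma by 0.42–0.49 SD, the standard error of the slope rises by √(1 + 0.25·d_S²) = 1.030/1.027/1.022, or about 2–3%. With no direct arm effect, simulated power falls from 0.81 to 0.78 (N = 104, d_S = 0.55, slope −0.28) and from 0.81 to 0.79 (N = 166, d_S = 0.42, slope −0.22).

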# Aim 2: Examine the relationship between PCC stigma and intention to get waivered, and likelihood of using Opioid Wizard.

**H2a:** Among non-waivered PCCs, PCCs who report lower stigma will report greater intention to get waivered to prescribe buprenorphine.

**H2b:** PCCs who report lower stigma will be more likely to use Opioid Wizard at flagged visits.

As secondary outcomes, we will gather additional objective measures of PCC behavior, including PCC prescribing and referral behavior and new waivers among previously non-waivered PCCs. In secondary analyses, we will examine if waiver status at the time of the intervention moderates the impact of the intervention on stigma attitudes and use of Opioid Wizard. Additionally, in exploratory analysis, we will examine whether stigma mediates the effect of the intervention on Opioid Wizard use and if receiving the stigma and/or control intervention increases the number of PCCs getting waivered or the number of patients receiving treatment (prescriptions or referrals for treatment). Results of this work will inform future interventions aimed at reducing stigma among PCCs for OUD and a variety of other stigmatized health conditions, including other SUDs.

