# E. Study Population

- a. Participants. Participants will be PCCs who practice at HealthPartners Clinics that have been previously randomized to the intervention arm of the parent study, Opioid Wizard. There will be 15 clinics randomized to receive the Opioid Wizard intervention. There are 225 eligible PCCs in the clinics randomized to the OUD-CDS. All randomized clinicians will be included in the analysis of Wizard use and prescribing and/or referral behavior (in event referrals are made to waivered clinicians).
- b. Inclusion and exclusion criteria. To be eligible for inclusion in this study, a PCC must practice at a study-eligible primary care clinic and be a family physician, general internist or adult-care non-obstetric nurse practitioner or physician assistant. PCCs are study-eligible regardless of whether they are waivered to prescribe buprenorphine.

**Sources or methods of recruitment.** For the parent study, PCCs will have the opportunity to participate in a webinar about general training of the Opioid Wizard tool. This webinar will include information about CDS alerts, printing the PCC and patient priorities, and using the tool within Epic's (EHR) active guidelines. At the end of the webinar, all eligible PCCs in intervention clinics will be notified about the opportunity to participate in additional case-based training on using Opioid Wizard, which they will receive an invitation to complete in their email. Up to three emails will be sent to PCCs from the MyLearning platform inviting them to participate in the training. The email will provide an introduction to the study and the elements of consent. We may also use additional strategies to encourage study participation, including asking clinic leaders to remind their PCCs to complete the training and directly emailing a final reminder before the initial survey closes. See **Appendix A** for recruitment email and **Appendix B** for the consent document. (Subsequent communications have been submitted separately as amendments.)

PCCs who complete the initial training via MyLearning (either the stigma reduction training or the comparison [attention control]) will be emailed a follow-up survey 3 months after they completed the initial training. PCCs will receive up to 4 emails to remind them to complete the follow-up survey. The recruitment email for the follow-up survey is available in **Appendix C**.

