#### F. Allocation of interventions

- **a. Methods for randomisation and stratification.** PCCs in clinics randomized to Opioid Wizard (in 15 of the 30 clinics randomized in the parent study) will be randomized 1:1 to the stigma reduction or comparison training, stratified by clinic and waiver status. Randomization will be generated using SAS software.
- b. Methods for concealment of allocation. PCCs will be blind to their randomized MyLearning training assignment. The study statistician ([name]) will generate the randomization assignment, and a study team member will submit that list to HP MyLearning staff. Study team members capturing outcome data from surveys, Opioid Wizard, and Epic (including use rates, buprenorphine prescriptions) will also be blind to treatment assignment.

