- iii. Intentions to prescribe buprenorphine should a waiver no longer be required. Non-waivered PCCs will be asked to rate one question on their intentions to get waivered to prescribe buprenorphine: "If your patient with OUD requested buprenorphine in the next year and a waiver were no longer required, would you prescribe buprenorphine?" PCCs will rate their response on a five-point Likert-type scale ranging from 1 (I definitely would not) to 5 (I definitely would). We have added this question given recent press reports that the federal government is considering no longer requiring a waiver to prescribe buprenorphine for physicians. Even if this potential rule change does not go into effect during this study, press coverage of this potential change could influence clinicians' intent to complete the waiver change (i.e., anticipating that soon it may no longer be required). The addition of this question provides a measure of intent to treat OUD with buprenorphine regardless of the waiver requirements at the time the question is answered. As noted above, moderate-to-large changes in

behavioral intentions are associated with small-to-moderate changes in behavior.

iv. Opioid Wizard Use. High use rates of Opioid Wizard are an important measure of PCC engagement. PCC Opioid Wizard use will be defined as taking action within the CDS tool, such as reviewing relevant chart history, screening for OUD, making a diagnosis, providing a referral or prescribing a medication, printing patient education materials, or prescribing naloxone. The use rates for each PCC for the follow-up period (6 months) will be calculated as the proportion of eligible visits in which Opioid Wizard was used. This provides an objective measure of PCC behavior with little social desirability bias.

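### The Aim 2 models adjust for neither clinic nor study arm: standard errors are too small if clinics differ on both stigma and the outcome, and the pooled slope can reflect the training itself

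*Combined protocol and SAP*

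**What the plan says.** Section M specifies multiple linear regression for H2a and H2b, "controlling for PCC characteristics (i.e., age, gender, PCC type [physician, nurse practitioner, physician assistant], and waiver status [H2b only". Section L agrees with that count: "For Aim 2, the regression models will include PCCs in both arms and up to 4 covariates". So the arms are pooled, and the list has no term for arm or clinic.

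Clinic is nevertheless part of the design. Section E states: "There will be 15 clinics randomized to receive the Opioid Wizard intervention". Under Section F, PCCs "will be randomized 1:1 to the stigma reduction or comparison training, stratified by clinic and waiver status". Section L describes the 30 parent-trial clinics "with an average of 15 per clinic (range 4-36". Section I uses clinic to describe completers and non-completers. No random effect, cluster adjustment or ICC appears anywhere.

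H2b is worded as an overall association: "PCCs who report lower stigma will be more likely to use Opioid Wizard at flagged visits". Its outcome is one value per clinician: "The use rates for each PCC for the follow-up period (6 months) will be calculated as the proportion of eligible visits". If H1d and H2b are both supported, Section M continues to mediation: "we will use a product of coefficients approach to quantify how much of the intervention effect is mediated by stigma". It does not list the terms in the stigma-to-use model.

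**The concern.** Stigma is measured, not assigned, so stratifying the randomization by clinic protects Aim 1 but not Aim 2. Two consequences are possible.

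- **Clinic.** Colleagues in one clinic may share attitudes and may share habits in using the tool. If both are true, an ordinary regression treats the PCCs as more independent than they are, and the Aim 2 p-values are too small.
- **Arm.** The training is meant to lower stigma and to raise intention and tool use. If it does both, a regression pooled over arms shows an association between stigma and outcome even where there is none among PCCs given the same training. H2b also gates the mediation analysis, where separating the effect of stigma from the direct effect of training is the whole purpose.

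**Working it through.** **Inputs from the documents.** Section L: 225 eligible PCCs; 112/146/180 participants at 50/65/80%; 93% non-waivered, so for H2a n = 0.93 x 112 = 104, 0.93 x 146 = 136 and 0.93 x 180 = 167; two-sided alpha 0.05; the Table 1 effects. Section E: 15 clinics.

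**Assumed.** The ICCs (equal for stigma and outcome), independent clinic effects, and individual clinic sizes.

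**Step 1: reproduce the Aim 2 rows of Table 1.**
- H2a: noncentral F test of one coefficient, lambda = f2 x n, error df = n - k - 1 with k = 4 to 6. At 80%/90% power, f2 = 0.077/0.103, 0.059/0.078 and 0.048/0.064, which round to all six printed values.
- H2b: n = (z_alpha/2 + z_beta)^2 exp(-B^2/2) / [base x B^2 x (1 - R2)], with B = ln RR and R2 = 0.05 (inferred from the match, not stated). At 30% use: RR = 1.599/1.706, 1.516/1.608 and 1.459/1.540. The 30%, 50% and 70% rows all agree with the table to within 0.01.

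Both formulas assume independent PCCs, so the sample-size section makes no allowance for clinic either.

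**Step 2: clinic.** The design effect for a slope is 1 + (m - 1) x ICC_stigma x ICC_outcome, with m = n/15. True type I error is 2[1 - Phi(1.96/sqrt(design effect))]. For example, at n = 167 and both ICCs 0.20, m = 11.1, the design effect is 1 + 10.1 x 0.04 = 1.40, and type I error is 0.098.

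| ICC (both) | Design effect, n = 104 to 167 | Type I error, formula | Type I error, simulated, n = 104/167 |
|---|---|---|---|
| 0.05 | 1.01-1.03 | 0.052-0.053 | 0.053/0.054 |
| 0.10 | 1.06-1.10 | 0.057-0.062 | 0.058/0.061 |
| 0.20 | 1.24-1.41 | 0.078-0.098 | 0.082/0.098 |

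Across equal and unequal clinic sizes and 50-80% participation, simulation gives about 0.05-0.06, 0.05-0.07 and 0.07-0.11. A linear model of the H2b use rate (assumed mean of 10 or 30 visits per PCC) gives 0.05-0.07 at ICC 0.10 and 0.06-0.11 at 0.20.

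The ICCs enter as a product, so if either is zero the design effect is 1. With only the outcome varying by clinic, simulated type I error was 0.048/0.047 (outcome ICC 0.10) and 0.049-0.051 (outcome ICC 0.20).

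**Step 3: study arm.** Suppose training lowers stigma by d_s and raises intention by d_i, in within-arm SD units, with 1:1 allocation and no stigma-intention link within arm. The pooled slope is -(d_s x d_i/4)/(1 + d_s^2/4). With the 80%-power effects for H1a and H1b in Table 1:
- 50%: -(0.49 x 0.55/4)/(1 + 0.49^2/4) = -0.0674/1.060 = -0.064
- 65%: -(0.47 x 0.48/4)/(1 + 0.47^2/4) = -0.0564/1.055 = -0.053
- 80%: -(0.42 x 0.44/4)/(1 + 0.42^2/4) = -0.0462/1.044 = -0.044

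In simulation the model without arm rejects in about 9-10% of trials. With arm included it rejects in about 5%. No ICC is needed here.

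**Step 4: mediation.** If training affects use only directly and arm is left out of the stigma-to-use path, the product of coefficients credits stigma with a share (d_s^2/4)/(1 + d_s^2/4) of the effect. For d_s = 0.42 this is 0.0441/1.0441 = 4.2%; for 0.49 it is 0.0600/1.0600 = 5.7%.

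**The case against.** The strongest case against the point is that the clinic effect is small and its size rests on assumed values. At ICC 0.05 the inflation is negligible. Clear inflation needs about 0.20 on both variables, and nothing in the documents supports that figure. This stands, and it limits the weight of the point. A reader might infer that any clinic difference makes the standard error too small; Step 2 shows that both stigma and the outcome must vary by clinic.

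A reader might also infer that the Aim 2 slope is wrong because it blends between-clinic and within-clinic association. At ICC 0.10, an assumed clinic-level correlation of -0.5 and no within-clinic association, the ordinary slope averages about -0.046 and is significant in 9-11% of runs. But Section C words H2a and H2b as overall associations, so blending is an error only if the within-clinic association is the target, which the plan does not say.

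On arm, the 9-10% rejection is not a false-positive rate for H2a as literally worded: if training moves both variables, the pooled association is genuinely non-zero. What stands is that it is confounded by training and says nothing about stigma among PCCs given the same training.

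On mediation, Section M does not say that the stigma-to-use path reuses the H2b covariates. The 4-6% applies only if it does, or if arm is otherwise left out.

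Finally, the random intercept does not help everywhere. At n = 104 and ICC 0.10 its simulated type I error is 0.059, against 0.058 without it. The gain appears with larger n or ICC: at n = 167 and ICC 0.20 it gives 0.052, against 0.098.

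**Conclusion.** The omission is real, and its consequences are conditional. The Aim 2 list leaves out clinic and arm, and nothing elsewhere in the plan makes up for it.

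- **Clinic:** the inflation is slight at ICC 0.10 or below and material near 0.20, and only when stigma and the outcome both vary by clinic. All ICCs are assumed.
- **Arm:** under the plan's own Table 1 effects and no within-arm link, the pooled H2a slope would be about -0.044 to -0.064 purely through training.
- **Mediation:** the plan is silent on arm; leaving it out would misattribute about 4-6% of a purely direct effect.

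A reader might infer that the Aim 1 results are compromised too. They are not: arms are randomized within clinic, and leaving the strata out of those models causes no bias and forgoes only a little precision. The point is minor and secondary to the randomized comparisons.

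**What to change.** In Section M:

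1. Add a clinic random intercept and study arm to the H2a and H2b models.
2. State that the stigma-to-use path of the mediation analysis includes arm and clinic.
3. Optionally, include the randomization strata in the Aim 1 models for a small gain in precision.

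Plain cluster-robust standard errors are a weaker substitute with 15 clinics: their simulated type I error ranged from 0.048 to 0.080 with independent clinic effects.

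As an optional sensitivity analysis, report within-clinic and between-clinic associations separately, using clinic-centred stigma plus the clinic mean, or clinic fixed effects. This matters only if the within-clinic association is of interest. If clinics do not differ, it costs about 3-7 points of H2a power; by the noncentral F calculation, fixed effects lower power from 0.82/0.81/0.82 to 0.76/0.76/0.79 at 50/65/80% participation.

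The main change is two or three sentences, using clinic and arm data already held from randomization. The random intercept has no measurable power cost: simulated H2a power is 0.78/0.79/0.80 with or without it. The arm term uses one degree of freedom and, at the Table 1 effects, removes the 4-6% of stigma variance that lies between arms. Specify these terms before the outcome data are examined, so that adding them is not a data-driven choice.
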